People who live with HIV (PLWH) experience a high incidence of neurocognitive deficits and HIV-associated non-AIDS (HANA) disorders, including cardiovascular disease (CVD), metabolic dysfunction, and autonomic decline. While antiretroviral treatment (ART) has reduced AIDS-related morbidity, both the virus and the medications are associated with lipid disorders that also increase CVD risk, including dyslipidemia and lipodystrophy. Consequently, the development of effective lifestyle interventions to reduce the incidence of HIV-associated neurocognitive disorders (HAND) and decrease metabolic disorders is a high priority. Physical activity (PA) has been utilized as an effective tool to improve health in PLWH, but may not be sufficient by itself to improve lipid levels. Existing PA interventions in PLWH typically required strenuous PA and significant resources that limit feasibility for many people living with the disease. Recent work indicates that interrupting periods of sedentary behavior (SB), independent of PA, also has a significant beneficial effect on metabolic function, but SB has not been well-studied in PWLH. Mediterranean-style diets (MedDiet) are also effective at improving CVD risk factors in HIV-uninfected individuals and are reported to reduce cognitive decline in persons at risk for Alzheimer's disease, but have not been widely tested in PWLH. We recently developed a novel and personalized Short Message Service (SMS) mobile phone text messaging intervention (iSTEP) that is designed to increase moderate PA in PLWH. Our objective is to expand upon this work and conduct an RCT examining the efficacy of iSTEP in combination with a mobile mHealth MedDiet intervention tailored to PLWH. 150 PLWH will be randomly assigned to a control group ($n = 50$), a 6-month iSTEP group with just a PA/SB intervention ($n = 50$), or a 6-month intervention with both PA/SB and MedDiet components ($n = 50$), where participants receive daily interactive SMS/MMS messages designed to increase moderate PA, reduce SB, and promote adherence to a MedDiet, including walnut consumption. PA/SB will be quantified by accelerometer, Fitbit step counts, and self-report, while MedDiet adherence will be assessed by self-report (Diet History Questionnaire and weekly SMS feedback) and also objective measures (polyunsaturated fatty acid levels - PUFA in blood). We will also conduct a follow-up assessment 6 months after the end of the intervention (accelerometer, neurocognitive testing, PUFA levels) to assess PA and MedDiet adherence. We hypothesize that iSTEP (both intervention arms) will increase PA, reduce SB, and improve neurocognition compared to control; the iSTEP + MedDiet group will demonstrate improvement in CVD risk factors and neurocognition compared to the PA intervention alone. Findings from this proposal will lay the groundwork for development of novel large-scale mobile PA/diet interventions dedicated to treating HAND and improving cardiovascular health for PLWH.

SCHEMA

iSTEP - an mHealth Physical Activity and Diet Intervention for Persons With HIV

DESIGN: Our objective is to assess the efficacy of a mobile phone text message intervention (iSTEP) designed to increase moderate physical activity (PA), reduce sedentary behavior (SB), and improve diet in people living with HIV (PLWH) in order to improve neurocognitive function and reduce cardiovascular disease (CVD) risk. This is a randomized RCT where participants are enrolled into one of three conditions: 1) a Control Group; 2) a PA intervention; 3) a PA + Diet intervention focused on encouraging a Mediterranean-style diet (MedDiet).

POPULATION: PLWH

STRATIFICATION: none

REGIMENT OR INTERVENTION

Assignment to 24-week control group, PA intervention, or PA + Diet Intervention

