5.0 STATISTICAL ANALYSIS PLAN

5.1. Analyses.

For all analyses, two-sided tests with significance level $\alpha=0.05$ will be used. Where necessary, assumptions for parametric testing will be checked prior to analyses. If assumption of normal distribution is not met, variable transformation (e.g., log) or nonparametric methods will be used. Randomization scheme should insure comparability of the groups on demographic and medical characteristics. Baseline characteristics will be compared between the groups using ANOVA for numeric values (e.g., age) and chi-square test for categorical variables (e.g., gender). Baseline characteristics found to be different between the groups will be used as covariates in the primary analyses to control for possible effect of group differences on the outcomes. For the primary analysis, PA outcomes will be measured at 2 visits (baseline (BL) and 24 weeks) with the exception of accelerometer and 7DPAR data, which will be measured at 3 visits (BL, 24 weeks, and 48 weeks); cognition and cardiovascular risk factors will also be assessed at 3 visits. Mixed models analyses will be conducted with a) the inclusion of all available data, assuming values missing at random; b) the baseline carry forward (BOCF) imputation method; and c) including only the participants who complete the study. For Hypothesis 1.1, changes in numeric outcomes measuring PA (e.g., time spent on PA, time spent on sedentary behavior) from baseline to week 24 (to week 48 for accelerometer/7DPAR measures) will be compared between the iSTEP and control groups using mixed effects models with subject-specific random effect. Subject-specific random effects will estimate individual changes in outcomes (slopes) as well as individual baseline values (intercept) to take into account natural variability in measured values between subjects. The models will regress PA measures on group (iSTEP vs. control), time (2 time points), and their interaction. A significant interaction term ($p<0.05$) would indicate a significant treatment effect or, in other words, significant differences in mean changes in outcomes over time (slopes) between the two treatment groups. Mixed effects model with terms for group, time (3 visits), and their interaction will be used to evaluate effect of iSTEP intervention on changes in accelerometer values. In explorative analysis, we will compare daily

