changes in PA variables measured daily (step count, time spent in PA, and time in SB) between iSTEP and control groups using similar method as above, except using many time points (days) instead of just 2 or 3. For Hypothesis 1.2, Global Mean T-score will measure cognitive performance at all visits; practice effect correction will be applied to values measured at the 24 and 48 weeks. Again, mixed effects model with subject-specific random effect will be used to regress T-score on group (iSTEP vs. control), time (3 time points), and their interaction. We hypothesize that a significant interaction term will show that the slope representing an improvement in cognition will be the smallest for the control group and the largest for the iSTEP group. Similarly, for Hypothesis 2.1, changes in multiple numeric outcomes related to cardiovascular disease risk factors (e.g., cholesterol) will be evaluated with separate mixed effects models. The models will regress the outcomes on group (control, iSTEP PA/SB, iSTEP PA/SB + MedDiet), time (3 time points), and their interaction, including subject specific random effect. We hypothesize that a significant interaction will be observed and that it will show greater improvements in the outcomes for iSTEP groups, with iSTEP PA + MedDiet group having the best results. Similar approach will be used for Hypothesis 2.2, were changes (slopes) in Global Mean T-scores will be compared between the iSTEP PA/SB + MedDiet and iSTEP PA/SB groups and between the iSTEP PA + MedDiet group and controls. Additional analyses: We will conduct exploratory analyses using mixed models to assess changes in diet markers (omega-3, DHA, EPA, percent fat intake on the DHQ) over time to assess if there are group differences and if these markers predict CVD/NP outcome. Multiple regression analyses will be conducted across all participants to examine which factors (PA amount, SB change, MedDiet Score) significantly predict NP and CVD risk factors, including metabolic measures and inflammatory markers at the 6-month and 12-month visits. We will collect Likert scale data that identify what aspect of iSTEP is most useful (e.g., step self-monitoring, step count goals, types of PA/SB messages, comparing PA data to other PLWH) and conduct regression analyses to identify factors (e.g., PA barriers, SMS adherence) that best predict study outcome and PA/diet maintenance.

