5.2 Power Analysis

For all power calculations 20% dropout rate is assumed based on prior mHealth diet interventions¹¹⁹, leaving N=40 for each of the three groups.

For mixed effects models comparing change in outcomes over time between groups, estimates of power depend on intra-class correlation (within-subject correlation of outcomes measured at different times) and number of total visits, including baseline. For models based on 2 visits (hypothesis 1.1, except accelerometer), there will be at least 80% power to detect a medium to large effect size, Cohen's d , for the difference in mean change in outcomes from baseline to week 24 visit (Fig 1a). For models based on 3 visits (accelerometer /7DPAR values in hypothesis 1.1; hypotheses 1.2 through 2.2), there will be at least 80% power to detect a large effect size, d , for mean differences in outcome changes over three visits between any of the two groups (Fig 1b).

[figure not shown]

Figure 1a. Comparing changes in PA outcomes between iSTEP group ($n = 40$ after 20% dropout) and controls ($n = 40$ after 20% dropout) from BL to week 24. **Figure 1b.** Comparing changes in accelerometer data, cardiovascular disease risk factors, or cognitive outcomes between iSTEP PA+MedDiet and either of the other two groups ($n = 40$ for each group after 20% dropout) from BL to 48 weeks.

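### If iSTEP means both arms in Hypothesis 1.2, a positive cognition result cannot be attributed to PA/SB, and no analysis explicitly names PA/SB alone versus control

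*Combined protocol and SAP*

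**What the plan says.** The abstract puts both active arms into the cognition hypothesis: "We hypothesize that iSTEP (both intervention arms) will increase PA, reduce SB, and improve neurocognition compared to control". Its next clause expects the combined arm to do better on neurocognition than PA alone.

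Section 5.1 tests Hypothesis 1.2 with a model that will "regress T-score on group (iSTEP vs. control), time (3 time points), and their interaction". It does not say which arms make up iSTEP. For Hypothesis 2.2, T-score changes are compared "between the iSTEP PA/SB + MedDiet and iSTEP PA/SB groups and between the iSTEP PA + MedDiet group and controls". The Figure 1b caption in section 5.2, which covers cognition, describes comparisons "between iSTEP PA+MedDiet and either of the other two groups".

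Other text points to a single arm. The abstract also describes the PA/SB-only arm as "a 6-month iSTEP group with just a PA/SB intervention ($n = 50"), and the Figure 1a caption gives the iSTEP group 40 participants after dropout, which is one arm and not two. The body of section 5.2 claims power, for Hypotheses 1.2 through 2.2, for a difference between any pair of groups. The Schema describes iSTEP as also meant to improve diet.

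**The concern.** Pooling the two active arms suits Hypothesis 1.1, because both receive the PA/SB component and the outcomes are PA and SB. Cognition is different. Half of the pooled group also receives the MedDiet, which the plan itself expects to improve cognition beyond PA/SB. A pooled contrast therefore mixes the two components.

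The two Hypothesis 2.2 contrasts do not separate them. The combined arm can beat both PA/SB and control while PA/SB does nothing. The comparison that answers whether PA/SB helps cognition is PA/SB alone versus control. Under the both-arms definition it is the one pair of the three that is not explicitly named. At stake is whether a positive Hypothesis 1.2 may be read as evidence for the PA/SB component.

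**Working it through.** **Inputs.** Section 5.1: "two-sided tests with significance level $\alpha=0.05$ will be used". Abstract: 150 randomised, 50 per arm. Section 5.2: "For all power calculations 20% dropout rate is assumed", "leaving N=40 for each of the three groups". Effect sizes below are in SDs of the change score. The text gives no number for a large effect, and the intra-class correlations are in a figure that is not available, so d = 0.8 is taken as large, with a range of 0.5 to 1.0.

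**The plan's own figures.** 50 × (1 − 0.20) = 40 per arm, as stated. For 40 v 40, the detectable d at 80% power is (1.960 + 0.842) × √(2/40) = 0.626 by the normal formula and 0.634 by the t-test. Power at d = 0.8 is about 94% to 95%. The claim of at least 80% power for a large effect is consistent with this. The Figure 1b curve itself cannot be checked.

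**What the pooled contrast estimates.** Let the mean change be 0 in control, a in PA/SB, and a + m in PA/SB + MedDiet. With equal arms, pooled minus control is (a + a + m)/2 = a + m/2. PA/SB alone minus control is a.

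**If PA/SB has no effect (a = 0, m = d).** The pooled difference is d/2, with standard error √(1/80 + 1/40) = 0.194. The normal formula gives:

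- d = 0.5: 0.25/0.194 = 1.29, power 25%.
- d = 0.8: 0.40/0.194 = 2.07, power 54%.

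This ignores the extra spread from mixing two arms with different means. A simulation of 100,000 trials per setting (40 per arm, t-tests on change scores) includes it. The share of trials significant in the favourable direction was:

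| MedDiet d | Pooled v control | PA/SB v control | Combined v PA/SB | Pooled positive, PA/SB v control not |
|---|---|---|---|---|
| 0.5 | 23% | 2.4% | 60% | 21% |
| 0.8 | 49% | 2.4% | 94% | 47% |
| 1.0 | 67% | 2.5% | 99% | 65% |

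The nominal one-direction rate for PA/SB v control is 0.05/2 = 2.5%.

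**Cost of the cleaner contrast.** The detectable d at 80% power for 80 v 40 is 2.802 × √(1/40 + 1/80) = 0.543 by the normal formula and 0.547 by the t-test. For 40 v 40 it is 0.626 and 0.634. The move is from about 0.55 to about 0.63. At 40 v 40, power is 61% at d = 0.5 and 95% at d = 0.8 (normal formula).

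**The case against.** The strongest reply is that Hypothesis 1.2 may already be PA/SB alone versus control. The abstract labels that arm the iSTEP group, Figure 1a gives the iSTEP group 40 participants, and the section 5.2 power text covers any pair. On that reading Hypotheses 1.2 and 2.2 together list all three pairs. A reader might infer from the abstract that the plan contains no comparison of PA/SB alone with control; the documents do not support so firm a claim. What remains is that this reading conflicts with the abstract's hypothesis, and that Figure 1a concerns PA outcomes rather than cognition.

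It can also be said that the model is nearly in place. Hypothesis 2.1 uses a three-level group term, and section 5.1 says Hypothesis 2.2 follows a similar approach, so the contrast may be estimable. That stands, but the contrast is still not named. The planned regressions on PA amount, SB change and MedDiet score are not randomised comparisons and cannot replace it.

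Third, the Schema counts diet as part of iSTEP, so calling a diet-driven result an iSTEP effect is not false on that definition. This stands too. The result would then describe any intervention, and the PA/SB question would remain open.

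Finally, a significant pooled test in the scenario above is not a false positive, since the pooled null hypothesis is untrue there. The problem is one of interpretation.

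**Conclusion.** The documents conflict on which arms form iSTEP in Hypothesis 1.2. Under the abstract's both-arms definition, no analysis explicitly names PA/SB alone versus control on the Global Mean T-score. The pooled contrast estimates the PA/SB effect plus half the added MedDiet effect, so a positive result could not be credited to PA/SB.

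A reader might go further and infer that a pure MedDiet effect would be declared an iSTEP effect. The figures do not support that: the chance is about 23% at d = 0.5 and 49% at d = 0.8, so up to d = 0.8 the diluted test misses such an effect at least half the time. Nor do the documents show that a PA-only programme would be carried forward; the abstract speaks of PA and diet interventions together.

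The figures assume 40 analysable per arm, equal variances, a change-score t-test and a PA/SB effect of exactly zero. The planned analysis is a three-visit mixed model, so they show the scale and are not exact operating characteristics. The a + m/2 result for equal arms does not depend on the assumed effect sizes. Confidence is moderate, because the point depends on how iSTEP is read; the change is worthwhile on either reading.

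**What to change.** State which arms form iSTEP in Hypotheses 1.1 and 1.2, and align the abstract, section 5.1 and the two figure captions. Pooling can stay for Hypothesis 1.1.

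For cognition, fit one three-level group model (control, PA/SB, PA/SB + MedDiet), as Hypothesis 2.1 already does. Prespecify PA/SB alone versus control on the Global Mean T-score as a named Hypothesis 1.2 contrast, alongside the two Hypothesis 2.2 contrasts, and add it to the Figure 1b caption. If the pooled contrast is kept, label it the effect of any intervention and do not use it as evidence for PA/SB.

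The cost is a change of wording, with no new participants or data. The detectable d for the PA/SB contrast is about 0.63, against 0.55 for the pooled one, which is still within the large effect that section 5.2 plans for if large is taken as 0.8.

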1.0 Introduction

HIV-associated neurocognitive disorders (HAND) remain a significant problem for PLWH and are linked to metabolic and cardiovascular disorders. Approximately 30-60% of persons living with HIV (PLWH) manifest some form of neurocognitive impairment, including deficits in executive function, attention, and memory collectively referred to as HIV-associated neurocognitive disorders (HAND)¹. Growing evidence indicates that metabolic syndrome (MetS) is an important factor that increases the risk and severity of neurocognitive impairment (NCI) in PLWH. MetS is frequent in PLWH, reported to be present in 47% of 2247 individuals during a 3-year period of participation in an AIDS Clinical Trials Group RCT study²⁵. MetS also increased the odds of neurocognitive decline in a sample of 643 PWLH patients with assessments at 6-month intervals²⁶. NCI severity in PLWH correlates with waist circumference (WC), a measure of abdominal obesity²⁷. Despite the efficacy of antiretroviral therapy (ART), PLWH continue to experience excess levels of morbidity and mortality linked to HIV-associated non-AIDS (HANA) disorders, including cardiovascular disease (CVD), metabolic dysfunction, and autonomic decline^{6, 7, 28}. CVD is now emerging as a major non-AIDS complication, with up to 20% of HIV+ individuals exhibiting a moderate to high 10-year risk of myocardial infarction (MI)²⁹. Contributing factors to CVD and MI risk include a pattern of lipid abnormalities, including increased serum triglycerides, lower high-density lipoprotein cholesterol (HDL-C), and higher low-density lipoprotein (LDL) cholesterol³⁰. PLWH also exhibit impaired autonomic nervous system (ANS) function indicated by decreased heart rate variability (HRV), a marker of poor vagal tone predictive of future CVD complications and higher rates of mortality^{31, 32}. While healthy individuals exhibit a high degree of HRV, reflecting the ability of the ANS to adapt quickly to physical or psychological challenges in the environment³³, reduced HRV persists in virus-suppressed PLWH taking ART and is linked to hypercholesterolemia^{34, 35}. CVD risk is also clearly increased by the use of ART itself, with a reported 26% relative increase in MI per year of ART exposure during the first 4-6 years of use³⁶. In summary, HAND, MetS, and elevated CVD risk are closely related and remain prevalent in PLWH; there is thus a significant unmet need to find effective strategies to address these ongoing issues⁵.

Physical Activity (PA) may provide many benefits for PLWH. PA provides a myriad of health benefits, including treating cardiometabolic disorders and improving HRV in persons with CVD, pulmonary disorders, and obesity³⁷⁻³⁹. Previous work in younger PLWH has shown that aerobic and resistance PA interventions improve fitness, reduce body fat, and normalize the lipid profile^{40, 41}. However, these studies involve rigorous PA conducted at gym facilities, a methodology that is not widely feasible for HANA treatment in PLWH with frailty and limited resources^{8-10, 42}. Although strenuous PA may not be suitable for many PLWH, increasing moderate PA, including walking, has significant health benefits and may improve metabolic and autonomic function⁴³⁻⁴⁶. For example, increasing step counts by 2,000-3,000 a day decreases total cholesterol⁴⁷, less than 3 hours of light PA per week reduces mortality for subjects with metabolic syndrome⁴⁸, and low-intensity walking also improves HRV^{39, 49}. CVD risk may be significantly reduced by modest lipid changes, e.g., increasing HDL-C by 5 mg/dL, reducing LDL-C by 10 mg/dL and triglycerides by 40 mg/dL, or lowering percent body fat by 1% and BMI by 1 kg/m²^{50, 51}; these effects can be achieved by moderate PA such as walking in HIV-uninfected persons⁵². However, exercise interventions in PLWH have also reported that PA may not improve lipid levels in a population challenged by both the virus and harmful side effects of ART²³; these data suggest that an intervention approach that targets multiple modalities (PA, diet) may be more optimal.

Sedentary behavior (SB) is not well-characterized or addressed in PLWH. Sedentary behavior

(SB), defined as sitting or reclining during waking hours with low energy expenditure (1.0 to 1.5 metabolic equivalents), is a distinct construct from PA and has recently been identified as a significant contributor to all-cause mortality, increased CVD risk, and poor metabolic function^{14, 53-55}. While moderate PA may occur during a small proportion of the day, adults in developed countries spend 55-70% of their time engaged in SB⁵⁴. Both the quantity and duration of SB intervals are related to metabolic health and have adverse cardiometabolic consequences even for physically active individuals^{14-16, 54, 56-59}. Every hour of daily sitting time is associated with a 2% increase in all-cause mortality, with a jump to 5% for sitting 7 or more hours per day⁶⁰. However, simply interrupting periods of SB, even with very short intervals (a break of 60 seconds or more) with light PA (standing, walking a few feet) has demonstrated benefits for metabolic function, including improvements in triglyceride levels, HDL-C, glucose metabolism, and insulin sensitivity^{43, 53, 55, 58, 61-63}. Unfortunately, SB has not been well-characterized in PLWH and little work has been done to modify this behavior in this population.

A Mediterranean-style diet (MedDiet) that includes walnut consumption may benefit both CV function and neurocognition. PLWH are reported to have poor diet quality, including higher fat consumption and lower fiber intake compared to HIV-uninfected individuals^{64, 65}. Several diet interventions focused on reducing saturated fat intake are reported to improve the lipid profile (reducing triglycerides, total cholesterol, and LDL-C levels)⁶⁶⁻⁶⁹, including significant improvements within a 6-month timespan^{66, 68}. However, limited changes have been observed for HDL-C, potentially resulting from an emphasis on reducing saturated fat (a traditional low-fat diet), but not on increasing exposure to polyunsaturated fats, in line with a MedDiet approach¹⁹. The primary MedDiet objectives include consumption of monounsaturated and polyunsaturated fat sources, fruits and legumes, and whole grains⁷⁰, including: 1) 3 or more servings of fish and seafood per week (a serving is generally equivalent to ½ to 1 cup of food); 2) 3 or more servings of nuts or seeds per week; 3) virgin olive oil for cooking (> 1 spoonful/day); 4) selected white meat (poultry); 5) fruit and vegetables (> 1 serving per day); 6) 2 or more servings of legumes per week; 7) whole grain breads. Eating white bread, white rice, red meat, processed pastries, cream and butter is discouraged. A large 12-month MedDiet study (PREDIMED) (7 years and 8000 participants⁷¹) randomized persons into 3 groups: a low-fat diet condition, a MedDiet group with an emphasis on virgin olive oil (VOO) intake, and a third MedDiet group with daily nut consumption (1 ounce per day of nuts, including walnuts). MedDiet administration led to many benefits, including: 1) a 30% reduction in CVD incidents for the MedDiet groups compared with the low-fat control^{72, 73}; 2) decreased oxidative stress^{74, 75}; 3) lower risk for CVD events generated by abdominal obesity⁷⁶; 5) improved cognition compared to the low-fat diet (Mini-Mental State Examination and Clock Drawing Test)⁷⁷. Importantly, other studies demonstrate that MedDiet improves metabolic function (lower cholesterol, triglycerides) after only 3 months⁷⁸.

Polyunsaturated fatty acids (PUFA), and omega-3 PUFA (n-3 PUFA) from sources such as walnuts may have significant benefits for brain health and cognition⁷⁹. Walnuts contain high levels of α-linoleic acid (ALA), which is converted to PUFAs such as eicosapentaenoic acid (EPA) and docosahexaenoic acid (DHA). These PUFAs contribute to brain health via several mechanisms, including stimulating neurogenesis, improving energy transport to the brain, reducing inflammation, and activating brain-derived neurotrophic factor (BDNF)^{80, 81}. Administration of walnuts (80 mg/day) to rats for 4-8 weeks improved cognitive performance on a radial arm water maze⁸², with optimal performance observed with a 6% walnut diet, equivalent to 1 ounce of daily walnut intake in humans (as with PREDIMED)⁷⁹. Nut consumption was also associated with improved working memory and reduced stroke risk in the PREDIMED cohort⁸³. Administration of n-3 PUFAs for 6 months also reduced cognitive decline in patients with Alzheimer's disease^{81, 84, 85}. Finally, preclinical studies indicate that combining PA and n-3

PUFAs may optimize cognitive improvement; DHA supplements enhanced the beneficial effects of exercise in rats (12 days) on cognition and BDNF-related synaptic plasticity⁸⁶; one week of exercise in rats combined with n-3 PUFA treatment increased markers of synaptic plasticity and glutamate receptor expression beyond either condition alone, biomarkers that correlated with improved performance on the Morris water maze⁸⁷. In summary, these findings suggest that a MedDiet approach augmented with walnut consumption, in combination with PA, may successfully reduce CVD risk and neurocognitive deficits in PLWH.

mHealth interventions improve PA and diet. Mobile health (mHealth) text messaging interventions have promoted a variety of health behaviors, including increasing PA and reducing body fat and cholesterol over periods as short as 12 weeks^{88 89-91}. Although Short Message Service (SMS) protocols have been developed to improve medication adherence in PLWH^{92, 93}, this methodology has not been utilized to promote PA or diet interventions in this population. In addition, few studies have specifically targeted SB in PLWH⁹⁴. Participant feedback has focused on three themes: adding a competitive component to iSTEP (allowing participants to compare their PA with others), being able to track their SB, not just steps, and the inclusion of diet as part of the intervention. Here we propose to conduct an mHealth intervention that examines the efficacy of a PA/SB intervention alone compared to PA/SB + MedDiet condition designed to improve neurocognitive performance and reduce CVD risk in PWLH with HAND and metabolic syndrome.

